3.1 Study Duration

Recruitment/enrollment is anticipated to begin in January, 2018 and will continue for ~48 months. We estimate that up to 110 participants will have completed the study by January, 2022. We estimate that it will take ~8 weeks/2 months for a participant to complete the in person component of the study, with the Follow-up survey occurring 1 month after study completion. Recruitment & Retention Pilot Study will conclude when all participants have completed the in-person visits for the study.

4 CHARACTERISTICS OF THE STUDY POPULATION

4.1 Target Population

4.1.1 Smoking Sample

Participants will be 80 healthy males and females between the ages of 18-65 who have smoked at least 5 cigarettes per day for the past 6 months,

4.1.2 Control Group

The non-smoking control group will consist of 30 individuals aged 18-65 reporting less than 100 lifetime cigarettes and not even a puff of a cigarette for a minimum of 2 years.

4.2 Accrual

We will enroll ~375 participants (i.e. provide consent) in order to have 148 participants eligible at the in-person intake. Of the ~148 anticipated eligible participants we expect that ~40% will attend all fMRI scans and complete the study (~80 smoking & 30 non-smoking participants). We plan to achieve this goal over a 48 -month enrollment period (3-4 participants/month). Accrual estimates are based on our extensive experience conducting neuroimaging studies and specifically recruitment of fMRI subsamples from larger clinical trials.

In order to increase retention throughout the study, we will: (1) educate subjects about the benefits of participation and the knowledge gained from the study; (2) schedule sessions at times convenient for participants; (3) provide reminders; and (4) provide payment for completion of all study visits. As is the convention in smoking cessation trials, smokers who are lost to follow-up will be included in the analysis and counted as smokers.

4.3 Inclusion Criteria

1. Male and female participants who are between 18 and 65 years of age.
 1. Smoking group – 80 smokers who self-report smoking at least 5 cigarettes (menthol and/or non-menthol) per day for at least the last 6 months. Smoking status will be confirmed by CO greater than or equal to 8 parts per million (ppm) at the Intake Visit.
 2. Non-smoking group - 30 individuals reporting fewer than 100 lifetime cigarettes and not even a puff of a cigarette for a minimum of 2 years. Smoking status of non-smokers will be confirmed by CO less than 5ppm. They will be matched to the smoker group on age, sex, and education.
2. Plan to live in the area for the duration of the study (i.e. ~8 weeks/2 months).
3. Capable of giving written informed consent, which includes compliance with the requirements and restrictions listed in the combined consent and HIPAA form.
4. Able to communicate fluently in English (i.e. speaking, writing, and reading).

CONFIDENTIAL

This material is the property of the University of Pennsylvania. Do not disclose or use except as authorized in writing by the study sponsor

4.4 Exclusion Criteria

Subjects who present and/or self-report with the following criteria will not be eligible to participate in the study:

Smoking Behavior

1. Regular use of nicotine-containing products other than cigarettes (e.g. chewing tobacco, snuff, snus, cigars, e-cigs, etc.). Participants agreeing to abstain from using nicotine-containing products other than cigarettes will be considered eligible.
2. Current enrollment or plans to enroll in another research and/or smoking cessation program over the duration of the study (i.e. ~8 weeks/2 months).
3. Anticipated use (within the next ~8 weeks/2 months) of any nicotine substitutes and/or smoking cessation treatments/medications unless provided through the study.
4. Provide a CO breath test reading less than 8 ppm at Intake Visit (smokers) or greater than 5ppm at intake visit (non-smokers).

Alcohol and Drug

- 1) History of substance abuse (other than nicotine) in the past 12 months and/or currently receiving medical treatment for substance abuse. Counseling and support groups (e.g. Alcoholics Anonymous and Narcotics Anonymous) will not be considered medical treatment for the purposes of this protocol.
- 2) Current alcohol consumption that exceeds 25 standard drinks/week.
- 3) Breath alcohol reading (BrAC) greater than .000 at the Intake Visit.
 - a) Participants testing positive for breath alcohol with a reading equal to or greater than .08 (the legal driving limit) or who are visibly impaired will be instructed not to drive themselves home after the appointment. If a participant needs to use a phone to call for a safe ride home, an office telephone will be made available to the participant.
- 4) A positive urine drug screen (UDS) for cocaine, opiates, amphetamines, methamphetamines, phencyclidine (PCP), ecstasy (MDMA), barbiturates, benzodiazepines, methadone, and/or oxycodone at the Intake Visit.

Medical

1. Women who are pregnant, breast feeding, or planning a pregnancy over the duration of the study period. Women must agree to use an adequate form of contraception or abstain from sexual intercourse for the duration of the study.
2. Current treatment of cancer or diagnosed with cancer (except basal or squamous-cell carcinoma not treated with chemotherapy and/or radiation) in the past 6 months.
3. Poorly controlled, brittle, or pump-dependent Type I diabetes.
4. Current peptic ulcer bleeding.
5. Active hepatitis or poorly controlled kidney and/or liver disease.
6. Serious or unstable disease within the past 6 months. Notable diseases will be evaluated on a case-by-case basis by the Principal Investigator and/or the Study Physician.
7. Any impairment including, but not limited to, visual, physical, and/or neurological impairments preventing proper completion of the study procedures. Notable impairments will be evaluated on a case-by-case basis by the Principal Investigator and/or the Study Physician.
8. Applicable food allergies or disorders:
 - Galactosemia ^a
 - Notable milk allergy (lactose intolerant participants may proceed unless they experience severe symptoms) ^b
 - Notable soy allergy ^c
 - Peanut allergy ^d

CONFIDENTIAL

This material is the property of the University of Pennsylvania. Do not disclose or use except as authorized in writing by the study sponsor

^{a,b,c} Boost® Original Very Vanilla Nutritional Shake: Contains milk and soy ingredients. Suitable for Lactose Intolerance.
^{a,b,c,d} M&M's® (Milk Chocolate): Contains milk and soy ingredients (MAY CONTAIN PEANUTS)
Lay's® Classic Potato Chips (Gluten Free): Potatoes, vegetable oil, and salt

Psychiatric

1. Current diagnosis of major depression. Subjects with a history of major depression, in remission for 6 months or longer (may be stable on antidepressant medications), are eligible.
2. Lifetime history of a suicide attempt.
3. Lifetime history of schizophrenia, psychosis, and/or bipolar disorder.
4. Current diagnosis of Attention Deficit/Hyperactivity Disorder (ADHD).
5. Current diagnosis of bulimia, anorexia nervosa or binge eating.

Medication

Current use or recent discontinuation (within the last 14 days) of:

1. Smoking cessation medication (e.g., Zyban, Wellbutrin, Wellbutrin SR, Chantix).
2. Benzodiazepines and/or Barbiturates.
3. Anti-psychotic medications.
4. Prescription stimulants (e.g., Provigil, Ritalin, Adderall).
5. Systemic steroids.
6. Medications for the use of addiction treatment.

Current use of:

7. Nicotine replacement therapy (NRT).
8. Heart medications such as digoxin, quinidine, and nitroglycerin.

Daily use of:

9. Opiate-containing medications for chronic pain.
10. Inhaled corticosteroids.

Subjects will be instructed to refrain from using any study-prohibited drugs/medications (both recreational and prescription) throughout their participation in the study. After final eligibility is confirmed, subjects who report taking contraindicated medication(s) over the course of the study period may only remain eligible if the Study Physician and Principal Investigator determine that the contraindicated medication(s) do/did not significantly impact the study design, data quality, and/or subject safety and welfare. Subjects are permitted to take necessary prescription medications not included within the exclusion list during the study.

General Exclusion

1. Past, current, anticipated, or pending enrollment in another research program over the study period that could potentially impact subject safety, study data, and/or the study design as determined by the Principal Investigator and/or Study Physician.
2. Participation in a dietary program within the past 30 days.
3. Any medical condition, illness, disorder, adverse event (AE), or concomitant medication that could compromise participant safety or significantly impact study performance as determined by the Principal Investigator and/or Study Physician. Subjects may be deemed ineligible for any of the aforementioned reasons at any point throughout the study, as well as during the initial telephone screen.
4. Significant non-compliance with protocol and/or study design as determined by the Principal Investigator and/or Study Physician. Subjects may be deemed ineligible at any point throughout the study.
5. Low or borderline intellectual functioning – determined by receiving a score of less than 80 on the Shipley Institute of Living Scale (SILS), which correlates with the Wechsler Adult Intelligence Scale-Revised (WAIS-R) Estimated IQ Test.

fMRI Exclusion Criteria

CONFIDENTIAL

This material is the property of the University of Pennsylvania. Do not disclose or use except as authorized in writing by the study sponsor

1. History of claustrophobia.
2. Lifetime history of stroke.
3. Having a cochlear implant or wearing bilateral hearing aids.
4. History of notable head trauma. Although notable head trauma is typically defined as being knocked unconscious for a period of three minutes or longer, notable head trauma will be evaluated on a case-by-case basis by the appropriate personnel prior to an eligibility decision, considering exceptions can be made based on the nature and severity of the trauma.
5. History of brain or spinal tumor.
6. Pacemakers, certain metallic implants or objects, or presence of metal in the eye as contraindicated for MRI.
7. Any circumstances (e.g., exclusionary metal implants, certain dental work, and/or physical impairments) and/or conditions that may interfere with MRI and MRI-related study visit procedures. All potential exclusionary circumstances and/or conditions will be evaluated on a case-by-case basis by the appropriate personnel prior to an eligibility decision.
8. History of gunshot wounds. Injuries from BB guns will be evaluated on a case-by-case basis by the appropriate personnel prior to an eligibility decision.
9. History of epilepsy and/or recurrent or uncontrolled seizures.
10. Weight greater than 275 lbs at Intake Visit or self-reported at phone screen. If a participant weighs less than or equal to 275 lbs at Intake, but presents with a weight greater than 275 lbs at either Scan 1 and/or Scan 2, the participant may be permitted to proceed with the scan as long as the participant's weight does not exceed 300 lbs.
11. A positive urine drug screen (UDS) for cocaine, opiates, amphetamines, methamphetamines, phencyclidine (PCP), ecstasy (MDMA), barbiturates, benzodiazepines, methadone, and/or oxycodone at intake or either Scan Visit.
12. A BrAC greater than 0.000 at intake or either Scan Visit.

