5.2.4 Mandatory Abstinence Period for Smoking Group (~days 1-3 or 29-31)

Participants will be randomized with respect to the order of the study periods; one-half of participants will have their mandatory abstinence period on days 1-4 and one-half will have this period on days 29-32. On the evening prior to the mandatory abstinence period, participants will receive a 20-minute structured telephone counseling session from a trained smoking cessation counselor to prepare for the upcoming 4-day abstinence period. Quit strategies include identifying triggers and alternative behaviors to smoking, deep breathing, and stimulus control methods. The abstinence periods will be framed as "practice quit attempts" unaided by nicotine replacement therapy or other medication.

On study days 1-3 (period 1) and 29-31 (period 2), participants will come to the Center and complete measures that may include a CO reading, breath alcohol test (BrAC), and questionnaires (smoking behavior, urges, mood, withdrawal, eating). Please see measures

CONFIDENTIAL

This material is the property of the University of Pennsylvania. Do not disclose or use except as authorized in writing by the study sponsor

table for specific time points. To verify smoking abstinence participants must have a CO reading of <10ppm or >50% reduction from their intake CO value on day 1 (or 29) and a CO reading of <5ppm on days 2, 3, or 4 (or 30, 31 & 32). Participants that do not meet CO criteria, have a BrAC greater than 0.000, or a positive urine drug screen will be withdrawn from the study, unless the Principal Investigator permits the participant to reschedule the visit to a later date.

Day 1/Day 29 Back-up Scheduling: Some participants may choose to be scheduled as a back-up for another participant's Day 1 or Day 29 visit. This is done to ensure that this protocol is efficiently using the time that is reserved on the fMRI scanner days at Days 4 and 32. Participants who are scheduled as a back-up should prepare for their back-up Day1/Day 29 in the same way that they would prepare for a primary visit. On the day of the back-up, participants should arrive at the Center in the smoking state that they have been assigned to for their respective Day 1/Day 29. Upon arrival participants will go through the same visit check-in to verify eligibility for the visit.

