Demographics, Smoking History, Cigarette Brand, and Nicotine Dependence (FTND)***: Standard questionnaires will be administered at the Intake Visit to collect the following data: demographics, age at smoking initiation, current smoking rate, previous quit attempts, and own cigarette brand information (Cigarette Brand Form). The Fagerstrom Test for Nicotine Dependence (FTND) will also be administered. The FTND is a 6-item, self-report measure of nicotine dependence derived from the Fagerstrom Tolerance Questionnaire. The FTND scale has satisfactory internal consistency (Cronbach's alpha = .64) and high test-retest reliability ($r=.88$).

Smoking Rate Timeline Follow Back (TLFB): A reliable and valid timeline follow-back method will be used to assess daily smoking (presence and rate) at every visit post Intake.

CONFIDENTIAL

This material is the property of the University of Pennsylvania. Do not disclose or use except as authorized in writing by the study sponsor

ETOH History***: An ETOH history questionnaire will be administered at the Intake Visit and will assess alcohol consumption over the past 7 days.

Shipley Institute of Living Scale (SILS)***: All participants will complete the SILS at the Intake Visit. The SILS is a self-administered test designed to assess general intellectual functioning in adults and adolescents and to aid in identifying cognitive impairments. The scale consists of two subtests: a 40-item vocabulary test and a 20-item test of abstract thinking. The total administration time is 20 minutes (10 minutes per subtest). A trained member of the study staff will score the test. The SILS correlates with the Wechsler Adult Intelligence Scale-Revised (WAIS-R) Estimated IQ Test; those participants earning less than an estimated WAIS-R IQ of 85 will be ineligible. The SILS is considered a highly reliable assessment tool with good total score internal consistency (Cronbach's alpha= .92).

Hunger Scale***: Immediately prior to and after completion of computerized laboratory tasks, participants will be asked to rate, "How hungry are you right now?" using a scale from 0 "not at all" to 10 "extremely."

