Eating Behavior (DEBQ)***: The Dutch Eating Behavior Questionnaire will assess restrained eating (10 items, tendency to restrict food intake), external eating (10 items, tendency to eat in response to food related cues) and emotional eating (13 items, tendency to eat in response to emotions). These scales are associated with food craving and response to food cues. Participants indicate on a Likert-style scale how often each item is applicable to them (0= not relevant; 1 = never to 5=very often).

Eating Inventory-Disinhibition (EI-D)***: Disinhibition will be measured with a subscale (16 items) of the Eating Inventory that is thought to reflect responsivity to environmental food cues, and internal cues, and linked to food reinforcement and weight change.

Carbon Monoxide (CO): CO will be measured at the Intake Visit for all participants and at all subsequent in-person visits to confirm smoking status of the smoking group. The CO monitor is a handheld device that uses a disposable mouthpiece, reports CO in parts per million (ppm), and takes about 3-5 minutes to administer.

Depression Symptoms (CES-D)***: The Center for Epidemiologic Studies Depression Scale is a 20-item Likert-style scale used to assess depressive symptomatology. This scale has high internal consistency ($r=.85-.90$) and has been shown to correlate with clinical ratings of the severity of depression. In our previous research, CES-D scores have correlated significantly with self-medication smoking and nicotine dependence.

Smoking Urges/Craving (QSU-B)***: The well-validated and reliable 10-item brief Questionnaire of Smoking Urges will assess craving for cigarettes. The QSU-B utilizes a "right now" frame of reference.

Weight Concerns***: Weight concerns associated with quitting smoking will be measured with a reliable ($\alpha=.87$) and valid 6-item scale. Responses to the 6 items range from 1 (not at all) to 10 (very much). Scores are the average of responses to all items.

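### The exception for users of other nicotine products covers both groups and is unchecked, so the non-smoker reference group may include nicotine users and substitution during abstinence could go unseen

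*Combined protocol and SAP*

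**What the plan says.** The first exclusion under Smoking Behavior in section 4.4 reads "Regular use of nicotine-containing products other than cigarettes (e.g. chewing tobacco, snuff, snus, cigars, e-cigs, etc". The sentence after it reverses this for some: "Participants agreeing to abstain from using nicotine-containing products other than cigarettes will be considered eligible". It names no group, no date from which abstinence counts, no minimum nicotine-free interval and no verification.

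Controls are defined in section 4.3 as "individuals reporting fewer than 100 lifetime cigarettes and not even a puff of a cigarette for a minimum of 2 years", and "Smoking status of non-smokers will be confirmed by CO less than 5ppm". Section 5.3.1 describes CO after Intake as taken "at all subsequent in-person visits to confirm smoking status of the smoking group". Table 2 agrees, marking every post-Intake CO and every TLFB entry as smokers only. The note to Figure 3 nevertheless promises controls the same monitoring as smokers.

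For smokers, section 5.2.4 rests verification on CO: "To verify smoking abstinence participants must have a CO reading of <10ppm" or a halving from the intake value on the first day, with a tighter cut-off afterwards. Of the TLFB, section 5.3.1 says "A reliable and valid timeline follow-back method will be used to assess daily smoking (presence and rate) at every visit post Intake".

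**The concern.** Aim 1 concerns intake during nicotine withdrawal, and section 5.2.4 intends abstinence without nicotine replacement. The exposure is therefore absence of nicotine, while the checks measure smoke. Two things are at stake.

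- **Reference group.** Section 5.6 uses non-smokers as the reference level for both Exploratory Aim comparisons (sated and abstaining smokers). A regular nicotine user among them affects both.
- **Abstinence state.** A smoker who replaces cigarettes with a non-combusted product would be analysed as abstinent. The mean differences between states, including caloric intake, the primary outcome, would move toward zero. The analyst would have no recorded variable with which to find or remove such cases.

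**Working it through.** **1. Can a nicotine user qualify as a control?** Take a daily e-cigarette or snus user who has smoked fewer than 100 cigarettes and none for two years. The lifetime count and the two-year condition both concern cigarettes, so both are met. CO at Intake reflects combustion, so a low reading is expected. Section 4.4 would exclude this person, but a stated agreement to abstain restores eligibility. By Table 2, no CO or TLFB follows in controls.

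**2. In what state would that control be scanned?** The control scan is on day 4. Intake is at about day -14 in section 5.2.2 and Table 2, but day -7 in Figure 3. If abstinence starts at Intake, the scan comes 4+14=18 or 4+7=11 days later. It could start later, since no date is set. If the promise is broken, the control is scanned while using nicotine.

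**3. Would anything reveal substitution by a smoker?**

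- CO (5.2.4): responds to combusted products, possibly cigars, but not to e-cigarettes, snus or nicotine replacement.
- TLFB (5.3.1): described as presence and rate of smoking.
- Urine panel (5.3.1): lists drugs of abuse and tricyclics, with no nicotine or cotinine.
- Tissue Specimens (5.4): urine only, for drug and pregnancy screens. Section 8.5 mentions saliva, but with no analyte or time point, and Table 2 has no saliva row.
- Covariates (5.6): other nicotine use is not among those named for Aims 1 and 2.

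**4. The plan's own power.** Inputs: n=80 smokers (General Design); two-sided tests; d=0.36 at 0.02 with 80% power for H1a and H1b, and d=0.32 at 0.05 for the effect of cessation on intake (both section 5.5). For a one-sample t-test on difference scores, power = P(|T| > t(1-alpha/2, n-1)), with T noncentral t, n-1 degrees of freedom and noncentrality d√n.

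- d=0.36: noncentrality 0.36×8.944=3.220, power 79.9%. The stated 80% reproduces.
- d=0.32: noncentrality 0.32×8.944=2.862, power 80.7%.
- With n=110, these become 92.0% and 91.4%, so the plan's figures rest on the 80 smokers.

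**5. Dilution, as an assumption.** Let a fraction f of smokers substitute fully and show no abstinence effect, with SD unchanged. Then d becomes d(1-f).

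| f | Smokers of 80 | d from 0.32 | Power at 0.05 | d from 0.36 | Power at 0.02 |
|---|---|---|---|---|---|
| 0% | 0 | 0.320 | 80.7% | 0.360 | 79.9% |
| 5% | 4 | 0.304 | 76.6% | 0.342 | 75.2% |
| 10% | 8 | 0.288 | 72.1% | 0.324 | 69.9% |
| 20% | 16 | 0.256 | 61.9% | 0.288 | 58.1% |

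**6. The Aim 1 slope.** Section 5.6 tests Aim 1 by regressing the intake difference on the BOLD difference. Assume a within-group slope of 0.40, unit SDs, mean shifts of 0.36 (BOLD) and 0.32 (intake), and 20% of smokers with no shift on either. The mixing term is 0.20×0.80=0.16, and the pooled slope is (0.40+0.16×0.36×0.32)/(1+0.16×0.36²)=0.4184/1.0207=0.41. It is not attenuated.

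**7. Controls.** Each misclassified control carries 1/30=3.3% of the reference mean; three carry 10%.

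**The case against.** The strongest reply is that the plan already forbids the behaviour. Section 4.4 bars current nicotine replacement and its anticipated use, readmitted users have promised to abstain, and significant non-compliance can end participation at any time. Participants also report past-24-hour smoking at Intake, Baseline and the scans, beyond the TLFB. The forms themselves are not in the documents, and staff must ask about other products to apply the exclusion at all. This stands as far as it goes: a smoker who substitutes breaks the protocol. But a prohibition acts only on what is detected, and no measure is described as asking about other nicotine after entry.

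Three stronger readings are tempting and are not supported.

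- A reader might infer that affected controls are scanned in nicotine withdrawal. The plan sets no start of abstinence, so the interval before the scan is unknown, and a control may instead still be using.
- A reader might infer that a dual user who keeps the promise spoils the smoking-as-usual state. A kept promise removes other nicotine from both periods and leaves cigarettes as the within-person contrast, which is a defensible reason for having the exception in smokers.
- A reader might take the power table as an estimate of loss. It has no prevalence behind it, and 20% would require 16 smokers to substitute fully and unseen.

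**Conclusion.** The gap is real on the text. Followed as written, the plan can place regular nicotine users in the 30-person reference group, and it describes nothing that would reveal non-combusted nicotine in the abstinence state.

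The control part affects only the Exploratory Aim, for which section 5.5 states no power. The smoker part affects mean abstinent-minus-smoking contrasts in caloric intake and BOLD; the direction, toward zero, assumes that substituters show a smaller abstinence effect. The size cannot be computed from the documents. The fall from 81% to between 77% and 62% at d=0.32 is an illustration conditional on 5% to 20% full substitution, no abstinence effect in those participants and unchanged SD. The Aim 1 slope need not shrink, as the example shows under its own assumptions. The case for an amendment rests on the eligibility and measurement wording, not on a demonstrated loss of power.

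**What to change.** 1. Limit the exception in section 4.4 to the smoking group. Define non-smokers by no regular use of any nicotine product, with the same two-year look-back as for cigarettes.
2. Add one item to the existing TLFB in smokers on use of e-cigarettes, smokeless tobacco, cigars and nicotine replacement, and flag any reported use on abstinence days. The sponsor should reconcile the handling of such days with the abstinence criteria in section 5.2.4. State that self-report is a partial check: it will not catch someone who conceals use.
3. Record regular non-cigarette nicotine use at Intake as a data field. Repeat the main contrasts without those participants and without flagged periods.
4. Reconcile the identical monitoring promised to controls in Figure 3 with the smokers-only CO and TLFB entries in Table 2.

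The cost is a wording amendment, one item on a form already in use, one Intake field and a sensitivity analysis. A few prospective controls would become ineligible. No new visit or assay is needed.
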